12.3. Device Deficiency

Device Deficiency Definition

A device deficiency is defined as inadequacy of the BioFire® and/or kits with respect to its identity, quality, durability, reliability, usability, safety or performance.

Device deficiencies include, but are not limited to, malfunctions, use errors, and inadequacy in the information supplied by the manufacturer including labelling.

A device deficiency may or may not be associated with an AE/SAE.

Reporting Device Deficiency

All device deficiencies related to devices in the procedure shall be documented throughout the study. The study site must report device deficiencies related to the BioFire and/or kits, within 48 hours after becoming aware of the event through the Device Deficiency form in the eCRF.

Manufacturer representatives will organize collection of the device for evaluation, as needed.

12.4. Deviations from the Clinical Study Protocol

A protocol deviation is any non-compliance with the study protocol, Good Clinical Practice. A deviation can be identified from a number of sources. Potential sources include, but are not limited to, a member of the Investigator's staff, a Sponsor representative during monitoring visits, or a member of the data management or statistical groups when entering or analysing data. Regardless of the source, it is crucial to document the deviation in the protocol deviation eCRF. The Investigator will report protocol deviations to the IRB/EC as required by the IRB/EC procedures.

Any deviation from the protocol or procedures should be recorded on the Deviation Form in the eCRF. Standard of care assessments not completed at a site should not be considered protocol deviations.

Steps to be taken to assure the accuracy and reliability of data include the selection of qualified investigators and appropriate sites, the review of protocol procedures with the Investigator and associated personnel prior to the study, and periodic monitoring visits by the Sponsor. The Sponsor will review eCRFs for accuracy and completeness during on-site and/or remote monitoring visits; any discrepancies will be resolved with the Investigator or designees, as appropriate.

12.5. Data Safety monitoring board (DSMB)

A Data Safety Monitoring Board has been established with the aim to safeguard the interests of trial participants, assess the safety of the interventions during the trial, and monitor the overall conduct of the trial. A specific charter document describes the roles and responsibilities of the independent DSMB for the ADEQUATE trial, including the timing of meetings, methods of providing information to and from the DSMB, frequency and format of meetings, statistical issues and relationships with other committees.

13. STATISTICAL CONSIDERATIONS

13.1. Sample size calculation

Co-primary endpoints used in the study:

1. Days on antibiotic treatment within 14 days (superiority endpoint)
2. Days alive out of the hospital within 14 days (superiority endpoint)
3. Adverse outcome within 30 days (non-inferiority safety endpoint)

Required sample sizes are presented for endpoint 2 and 3. Endpoint 1 is non-limiting due to having an expected smaller standard deviation compared to endpoint 2 and having the same clinically relevant effect size.

The intervention is considered successful if superiority is demonstrated for either or both endpoints 1 and 2 AND non-inferiority is demonstrated for endpoint 3. We use a hierarchical nested design: superiority primary endpoints are tested first. Only if superiority to at least one of the two superiority endpoints is confirmed, the non-inferiority safety endpoint is taken into consideration. To maintain an overall alpha < 0.05, the two superiority endpoints will be tested using a two-sided alpha of 0.025, while the non-inferiority endpoint will be tested using a one-sided alpha of 0.05. The minimal power for the superiority endpoints is set to 0.9 and for the non-inferiority endpoint to 0.95. This is to maintain overall power of the trial, given the hierarchical testing. For 'Adverse outcome' we considered different non-inferiority margins. For 'Days on antibiotic treatment' and 'Days alive out of the hospital' we defined 1 day as a clinically relevant effect size.

The distribution of endpoint 2 is yet unknown for the ARI population. We supported our sample size calculation using data of patients presenting with CAP to Dutch ERs and hospitalised to a non-ICU ward (ClinicalTrials.gov: NCT02604628). The standard deviation (SD) of 'Days alive out of the hospital within 14 days' in this population was 4 days. The theoretical maximum SD with a 14 days follow-up period is 7 (which would be the case if 50% had zero days and 50% had 14 days alive out of the hospital). However, we expect that in the target population the variability for this endpoint will be less than in the CAP population. We varied the SD to assess the impact on

the sample size. We used a standard correction factor of 1.15 for non-normality of the data. (Table 1) Hence for the superiority endpoints a sample size of 457 per arm would be adequate.

Table 1: Sample sizes for Days alive out of the hospital using different assumptions

SD	Relevant effect size	Alpha	Beta	Correction	Sample size per arm
3	1	0.025	0.1	1.15	257
4	1	0.025	0.1	1.15	457
5	1	0.025	0.1	1.15	714
6	1	0.025	0.1	1.15	1,028
7	1	0.025	0.1	1.15	1,399

For adverse outcome, if we assume an incidence of 10% the sample size would be 780 per arm, and if we assume 5% it would be 412, in both cases using a non-inferiority margin of 5% (Table 2). A high power for adverse outcome is considered important because both the superiority and the non-inferiority hypothesis need to be confirmed in order to declare the intervention a success so a total of 780 adults per study arm would be required to reach 95% power

Table 2: Sample sizes for adverse outcome using different assumptions.

Incidence *	Non-inferiority margin	Alpha**	Beta	Sample size per arm
0.05	0.05	0.05	0.05	412
0.10	0.05	0.05	0.05	780

* same for intervention and control arm; ** one-sided alpha

To account for potential drop-outs we will aim for a **total of 1600 adults** in the study. The sample size includes participants that are randomised and does not include enrolled but non-randomised patients.

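### The two superiority endpoints stay at two-sided 0.025 even after the other is won; a Holm step-down, tied to the non-inferiority result, is a free but mostly small gain

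*Combined protocol and SAP*

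**What the plan says.** Section 13.1 of the protocol has two superiority endpoints, days on antibiotics and days alive out of hospital (both within 14 days), and one non-inferiority endpoint, adverse outcome within 30 days. Its success rule is: "The intervention is considered successful if superiority is demonstrated for either or both endpoints 1 and 2 AND non-inferiority is demonstrated for endpoint 3".

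On error control it gives the aim "To maintain an overall alpha < 0.05". Days on antibiotics and days alive out of hospital get the same fixed level: "the two superiority endpoints will be tested using a two-sided alpha of 0.025". Adverse outcome has its own level, 0.05 one-sided.

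The hierarchy described in sections 7.1 and 13.1 runs from the superiority pair to the safety endpoint: "Only if superiority to at least one of the two superiority endpoints is confirmed, the non-inferiority safety endpoint is taken into consideration". The two superiority endpoints are not ordered, and no alpha passes from one to the other. Section 13.2 leaves a statistical analysis plan to be prepared later; the text available contains no step-wise rule.

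**The concern.** This is a plain Bonferroni split. Once one superiority endpoint is significant at 0.025, the other can be tested at 0.05 without taking the familywise error of the pair above 0.05. The plan holds it at 0.025 all the same.

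Section 5.1 asks about hospital days and antibiotic days as separate objectives, so the second result matters in its own right. Under the present rule, a second endpoint with a p-value between 0.025 and 0.05 would be reported as not shown, although the error budget for the pair would allow the claim.

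**Working it through.** **Inputs from section 13.1.** Two-sided alpha 0.025 per superiority endpoint; "The minimal power for the superiority endpoints is set to 0.9 and for the non-inferiority endpoint to 0.95"; for both superiority endpoints, "we defined 1 day as a clinically relevant effect size"; SD 4 days for days alive out of hospital; correction factor 1.15; 780 per arm, set by the non-inferiority endpoint.

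**Assumptions not in the documents.** The correlation between the two test statistics, each oriented so that positive means benefit, is taken as 0.4, with 0 to 0.7 as the range. No SD is given for antibiotic days, only that it is expected to be smaller; it is set equal to the other SD unless stated.

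**Step 1: the plan's figures reproduce.**
- Superiority: 1.15 × 2 × [4 × (2.2414 + 1.2816) / 1]² = 456.7, so 457 per arm. The other rows of the sample-size table also reproduce (257, 714, 1,028, 1,399).
- Non-inferiority: 2 × 0.10 × 0.90 × (1.645 + 1.645)² / 0.05² = 779.2, so 780. At 5% incidence the same formula gives 412.

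**Step 2: type I error of the superiority pair.** The fixed split totals 0.025 + 0.025 = 0.05 (0.0494 if independent). With one endpoint truly effective and the other null, the fixed split spends 0.025 on the null endpoint. Holm spends up to 0.05, still within the limit. With no effect on either endpoint, the two rules have the same error.

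**Step 3: power.** The expected test statistic is d / [SD × √(2 × 1.15 / n)]. For d = 1, SD = 4 and n = 780 it is 1 / 0.2172 = 4.604. Power for one endpoint is then Φ(4.604 − 2.241) = 99.1% at 0.025 and Φ(4.604 − 1.960) = 99.6% at 0.05. For d = 0.5 the statistic is 2.302, and power is 52.4% and 63.4%.

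Both effects are proved under the fixed split if both statistics exceed 2.241. Under Holm, both must exceed 1.960 and at least one must exceed 2.241. From the bivariate normal distribution, 780 per arm, correlation 0.4:

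| Scenario | Both proved, fixed 0.025 | Both proved, Holm |
|---|---|---|
| Plan's case: 1 day on both, SD 4 | 98.3% | 99.2% |
| 1 day on both, SD 5 | 87% | 92% |
| 1 day on both, SD 6 | 67% | 77% |
| 1 day and 0.5 day, SD 4 | 52% | 63% |
| 0.5 day on each, SD 4 | 34% | 45% |

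With an antibiotic SD of 3 and a hospital SD of 4, the plan's case moves from 99.1% to 99.6%. Over correlations 0 to 0.7 the gain is 0.8 to 1.0 point in the plan's case, 4.4 to 6.0 points at SD 5, 8.2 to 11.2 at SD 6, about 11 for 1 day and 0.5 day, and 10.0 to 11.5 for 0.5 day on each.

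**Step 4: at least one win.** Holm tests the smaller p-value at 0.025, exactly as the fixed split does. The chance of at least one win is therefore identical, and so is the chance of reaching the non-inferiority test.

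**Step 5: the non-inferiority gate.** The safety test opens after a single superiority win. Take one endpoint effective, the other null, adverse outcome exactly at the margin, and independent tests. If superiority and non-inferiority are read as separate claims, the chance of any false claim is 1 − 0.975 × 0.95 = 7.4% under the plan and 1 − 0.95 × 0.95 = 9.8% under Holm alone. If a superiority claim counts only together with non-inferiority, every false claim in this setting needs a false non-inferiority result, so the rate is 5.0% under either rule. When the intervention really is non-inferior, only the superiority pair can err, and Holm holds that at 0.05.

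**The case against.** The strongest reply is that a fixed split is valid, conservative and transparent, and that the trial is large enough for the loss hardly to matter. Much of this stands.

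- **Size under the design.** The safety endpoint raises the trial from 457 to 780 per arm, so each superiority endpoint already has about 99% power at 0.025. Section 13.1 also expects less variability than in the pneumonia population behind the SD of 4. Gains of about 10 points or more need an SD of 6 or an effect of half the day that the plan calls relevant. Against this, the same section says the distribution of days alive out of hospital is not yet known and tabulates SDs up to 7, and section 13.5 foresees that the assumptions may need checking.
- **The trial verdict.** A reader might infer that the split puts overall success at risk. It does not: success needs only one superiority win plus non-inferiority, and Holm changes neither. Hochberg's procedure could also rescue a trial with both p-values between 0.025 and 0.05. That adds about 1.3 points to the chance of any win at 0.5 day on each endpoint (about 71% to 72%), and next to nothing in the plan's case (99.92% to 99.94%).
- **Overall alpha.** A reader might also infer that Holm can be inserted with no further wording. Step 5 shows that this holds only if the superiority claims are tied to non-inferiority. The success rule already joins them, so the condition fits the plan, but it must be written down.
- **Intervals.** Section 13.3 foresees bootstrap confidence intervals. A fixed 0.025 pairs directly with a 97.5% interval for each endpoint; a step-wise test has no equally simple match. This is a real, minor cost.

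**Conclusion.** The point holds as a free improvement, not as an error in the plan. The fixed split controls the error of the superiority pair; Holm controls it equally and can only add rejections. The gain in the chance of proving both effects is about 1 point under the plan's own assumptions, and 5 to 11 points if the SD is 5 to 6 or an effect is half a day. The documents do not support reading this as a threat to trial success or as a substantial loss under the design.

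These figures rest on the normal approximation with the plan's 1.15 correction, 780 per arm, the assumed correlation of 0.4 and the assumed SD for antibiotic days. The error control of Holm over the pair does not depend on the correlation.

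**What to change.** In section 13.1, replace the rule for the two superiority endpoints with, for example:

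> *The smaller of the two superiority p-values is tested at two-sided 0.025; if significant, the other is tested at two-sided 0.05 (Holm). A superiority claim on either endpoint counts only if non-inferiority on adverse outcome is also shown (one-sided 0.05).*

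Carry the same wording into the statistical analysis plan before any comparison by arm, and say there how the reported confidence intervals relate to the step-wise test.

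The cost is these two sentences and slightly less simple intervals. No patients are added, and the sample size, both sample-size tables in section 13.1 and the non-inferiority test do not change.

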13.2. Analysis populations

A statistical analysis plan will be prepared after protocol approval and once site selection process has been initiated.

The main analyses will be performed for the total population

Analyses will be stratified by:

- age groups (i.e. 18-49, 50-65, >65)
- clinical syndrome: exacerbation of chronic pulmonary disease, influenza-like illness, laryngitis/laryngotracheitis (croup), acute bronchitis
- risk factors. Patient groups at risk for developing severe disease are well known, such as the elderly, patients with chronic pulmonary, cardiovascular or metabolic disease or immunocompromised patients. Clinical predictors of severity are also well known. Still,

within risk groups may exist the uncertainty whether to hospitalise and/or to treat and the impact of testing may be assessed.

- Vaccination status. Influenza. Pneumococcal.

The primary analysis will follow the intention-to-treat principle in which groups are compared based on the allocated regimen. In the per protocol analysis we will exclude participants not receiving the test according to the randomised regimen (e.g. randomised to rapid syndromic testing but not receiving the test).

13.3. Primary study parameter(s)

Descriptive statistics will be produced and tabular summaries will be presented, stratified according to the allocated group (rapid syndromic testing vs. control). Categorical data will be summarized by the number and percentage of patients in each category. Appropriate summary statistics will be used for continuous variables depending on the distributional assumptions. These include measures of central tendency (mean or median) and dispersion (standard deviation or inter-quartile range).

‘Days on antibiotic treatment’ and ‘Days alive out of the hospital’ will be analysed using a linear regression analysis, including as covariates stratification by age groups and predefined risk factors. Upfront we may expect that the assumption of normally distributed residuals is violated, in which case we will determine the confidence interval by bootstrapping.

Adverse outcome will be analysed using Cox proportional hazards regression adjusted for age groups and predefined risk factors. Risk differences and 90% CI will be inferred by comparing the cumulative incidence of failure at day 30 from the Cox model and bootstrapping for the confidence interval. A 90% CI will be used to be compatible with a one-sided alpha of 0.05.

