4. BACKGROUND AND RATIONALE

4.1. Background

Community-acquired acute respiratory infections (CA-ARTI), including upper and lower respiratory tract infections, are among the most frequent infectious diseases worldwide. Lower respiratory tract infections (LRTI) are among the most lethal communicable diseases and the fourth cause of death globally, responsible for an estimated 3 million deaths in 2016 [1]. LRTI disproportionately affects children younger than 5 years and is the second cause of disability adjusted life years (DALYs). A study published in the Lancet in 2018 estimated the global, regional, and national morbidity, mortality, and aetiologies of LRTI in 195 countries, between the years 1990–2016. In 2016, LRTI caused 652,572 deaths (95% uncertainty interval 586,475–720,612) in children younger than 5 years, 1,080,958 deaths (943,749–1,170,638) in adults older than 70 years, and 2,377,697 deaths (2,145,584–2,512,809) in people of all ages, worldwide. *S. pneumoniae* was the leading cause of LRTI morbidity and mortality globally, contributing to more deaths than all other aetiologies combined in 2016 (1,189,937 deaths (690,445–1,770,660)[2], particularly as community acquired pneumonia. Within the European region, geographical variations are present. Over the years, the epidemiology has changed due to changing populations, with increased disease burden in elderly (>70 years) in many regions, varying prevalence of smoking and varying patterns of vaccine usage [3, 4].

On the other hand, uncomplicated ARTI is the most frequent cause of inappropriate antibiotic use [5, 6], and there is a need of more judicious antibiotic prescription to prevent exposure to drug-related adverse events, selection of antibiotic resistance and emergence of opportunistic pathogens that substitute the indigenous microbiota. At the same time, the clinical role of bacteria whose normal ecological niche is in the airways is an unresolved issue because of contamination with oropharyngeal flora. Antibiotic resistance rates are related to antibiotic use in any setting, but opportunities to decrease unnecessary treatments are probably most apparent in primary care and emergency departments. Not only the ecological but also, the economic cost of antimicrobial

resistance per antibiotic consumed is considerable [7-9]. Management is heterogeneous in diverse geographical areas due to non-uniform guidelines, both for diagnostic and antimicrobial stewardship [10].

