8.4. Recommended Study site selection criteria

- Does not currently use equivalent rapid testing routinely in patients with CA-ARTI at the ER (rapid defined as time from sample collection to result interpretation by the physician within 4 hours).
- At least 25% of CA-ARTI patients seen at ER are not hospitalised.
-
- Microbiology lab is capable of performing molecular testing.
- Highly motivated and GCP-trained local Principal Investigator. Clinical research nurse.
- **Geographical balance:** We will prioritize EU Member States and H2020 Associated Countries with **high and medium antibiotic use** and with a range of **country level income and antibiotic stewardship programs** (if present, the antibiotic stewardship program will be documented, including the list of participant roles). Variations in **microbiological aetiologies and vaccination policies** will be taken into consideration.

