10.2. Randomisation and blinding

Due to the nature of the intervention, blinding is not possible. After all eligibility criteria have been verified and informed consent has been obtained, randomisation will be performed using the built-in randomisation module of the eCRF system. Allocation will be concealed until the moment of randomisation. To this end, block randomisation will be used with variable blocks of size 2, 4 and 6. Randomisation will be stratified by centre. After the decision to randomise the patient is made, patients will not be excluded from the trial. If the allocated intervention is not applied for any reason, this will be recorded and follow-up for the participant will be completed.

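### Randomisation is stratified by centre, but the primary models leave centre out; if centre is prognostic, the confidence intervals are wider than the design warrants

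*Combined protocol and SAP*

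**What the plan says.** On allocation, Section 10.2 states "Randomisation will be stratified by centre" and adds that "block randomisation will be used with variable blocks of size 2, 4 and 6". No other stratification factor is named.

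On analysis, Section 13.3 says that antibiotic days and days alive out of hospital "will be analysed using a linear regression analysis, including as covariates stratification by age groups and predefined risk factors", with a bootstrap interval if residuals are not normal. For the safety endpoint it says: "Adverse outcome will be analysed using Cox proportional hazards regression adjusted for age groups and predefined risk factors". The day-30 risk difference and its 90% interval are then obtained from the Cox model by bootstrapping. Centre appears in neither model, and neither bootstrap is described as resampling within centre.

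The risk factors described in Section 13.2 are patient characteristics such as older age, chronic disease and immune compromise, so they do not bring centre in by another route. The only analysis by type of hospital is exploratory (Section 5.3).

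Section 13.2 also says: "A statistical analysis plan will be prepared after protocol approval and once site selection process has been initiated". That plan is not among the documents, so this point concerns the model text in the protocol that the SAP would follow.

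**The concern.** Stratified blocks keep the arms nearly balanced within each centre, so differences between centres largely cancel out of the treatment comparison. The sampling variance of the estimate is reduced accordingly. A regression without centre, or a bootstrap that resamples patients regardless of centre, still counts those differences as noise. The reported standard error then exceeds the true one, intervals are too wide, and tests run below their nominal level.

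How much this matters depends on how prognostic centre is. The protocol gives reasons to expect some effect. Section 4.1 says "Management is heterogeneous in diverse geographical areas due to non-uniform guidelines, both for diagnostic and antimicrobial stewardship", and Section 8.4 seeks sites with a range of "country level income and antibiotic stewardship programs". Two of the three primary endpoints, antibiotic days and days out of hospital, depend directly on local prescribing and admission practice.

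What is at stake is precision. No false claim of superiority or non-inferiority becomes easier.

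**Working it through.** **Inputs from the documents.** Section 13.1 gives a two-sided alpha of 0.025 for each superiority endpoint (z = 2.2414) and a one-sided 0.05 for non-inferiority (z = 1.645). On effect size, "we defined 1 day as a clinically relevant effect size". The planning SD is 4 days, with 3 to 7 tabulated, and the non-normality factor is 1.15. Adverse-outcome incidence is 10%, the margin 5 points, and n = 780 per arm. Section 7.1 gives up to 10 sites.

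**Assumption.** ICC is the share of outcome variance lying between centres. The documents give no value; 0.01 to 0.20 is shown. It should be read as the share left after adjustment for age and risk factors. Total SD is held fixed.

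**Step 1: reproduce the plan's sizes.**
- Superiority: n = 2 × SD² × (2.2414 + 1.2816)² × 1.15. For SD 3, 4, 5, 6 and 7 this gives 257, 457, 714, 1,028 and 1,399, as in the protocol.
- Non-inferiority: n = 2p(1 − p)(1.645 + 1.645)² / 0.05². For p = 5% and 10% this gives 412 and 780, as in the protocol.

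**Step 2: standard error and test level without centre.** True SE = model SE × √(1 − ICC). The SE is therefore overstated by a factor 1/√(1 − ICC). The actual two-sided level is 2 × [1 − Φ(2.2414/√(1 − ICC))], and the one-sided level is 1 − Φ(1.645/√(1 − ICC)).

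| ICC | SE overstated by | Actual level, nominal 0.025 | Actual level, nominal 0.05 (non-inferiority) |
|---|---|---|---|
| 0.01 | 0.5% | 0.024 | 0.049 |
| 0.05 | 2.6% | 0.021 | 0.046 |
| 0.10 | 5.4% | 0.018 | 0.041 |
| 0.20 | 11.8% | 0.012 | 0.033 |

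**Step 3: superiority power for 1 day at 780 per arm.** Model SE = √(2 × SD² × 1.15/780), which is 0.217 at SD 4, 0.272 at SD 5 and 0.326 at SD 6. Power without centre = Φ((1 − 2.2414 × model SE)/true SE). Power with centre = Φ(1/true SE − 2.2414). Entries are without/with centre.

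| ICC | SD 4 | SD 5 | SD 6 |
|---|---|---|---|
| 0.01 | 99.1/99.1% | 92.6/92.8% | 79.7/80.0% |
| 0.05 | 99.2/99.3% | 93.0/93.8% | 80.2/81.8% |
| 0.10 | 99.4/99.5% | 93.6/95.0% | 80.9/84.0% |
| 0.20 | 99.6/99.8% | 94.7/97.0% | 82.3/88.3% |

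**Step 4: non-inferiority, using a binary approximation to the Cox-based risk difference.** Model SE = √(2 × 0.1 × 0.9/780) = 0.0152, so the 90% interval half-width without centre is 1.645 × 0.0152 = 2.50 points. Power without centre = Φ((0.05 − 1.645 × model SE)/true SE). Power with centre = Φ(0.05/true SE − 1.645).

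| ICC | Half-width with centre (points) | Power without/with centre |
|---|---|---|
| 0.01 | 2.49 | 95.1/95.2% |
| 0.05 | 2.44 | 95.4/95.8% |
| 0.10 | 2.37 | 95.9/96.6% |
| 0.20 | 2.23 | 96.7/97.9% |

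**Step 5: simulation of the superiority test under no effect.**
- With 10 unequal centres of 50 to 300 patients, N = 1,560, blocks of 2, 4 and 6, and 10,000 replicates, rejection rates without/with centre were 0.0236/0.0241, 0.0202/0.0247, 0.0156/0.0214 and 0.0131/0.0275 at the four ICCs (Monte Carlo SE about 0.0015).
- A separate simulation with 4,000 runs at ICC 0.20 gave a mean model SE of 0.1995 against an empirical 0.1797 without centre, and 0.1810 against 0.1798 with centre. At ICC 0 the two analyses agreed.

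Both simulations show the test without centre to be conservative. With centre, rejection rates scatter around the nominal level.

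**The case against.** The strongest reply is that this is ordinary SAP content. The SAP is deferred, is to be shared with the paediatric protocol (Section 3), and may well include centre. That is fair. It limits the point to a recommendation for the SAP, but the protocol as written specifies models without centre.

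Second, the effect is small and conservative, and the sizeable power gain needs a large SD and a high ICC together, while Section 13.1 expects an SD below 4. This also stands. Section 13.1 does say that the distribution is unknown in this population, and it tabulates SDs up to 7.

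Third, the higher ICCs are less plausible for adverse outcome. At 10% incidence the between-centre SD of risk is √(ICC × 0.09), which is 3.0 points at ICC 0.01 and 6.7 at 0.05, but 9.5 at 0.10 and 13.4 at 0.20. The documents do not suggest so wide a spread, so the first two non-inferiority rows deserve the most weight. At 5% incidence with 780 per arm, power is at least 99.8% either way.

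Fourth, small centres could be unstable. At 5% incidence, 1,560 patients give about 78 events, or 78/20 ≈ 4 per centre and arm with 10 equal centres. Enrolment is competitive, so some cells will hold fewer. This is a reason to pre-state a pooling rule; it is not a reason to omit centre.

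**Conclusion.** The concern holds as a loss of precision with no fault of validity. Centre is the sole stratification factor and is absent from both primary models and both bootstraps. If centre is prognostic after adjustment for age and risk factors, intervals are too wide by 0.5% to 5.4% for ICCs of 0.01 to 0.10, and by 11.8% at 0.20. If the assumed ICC is instead a raw one, these figures are upper bounds.

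Type I error stays at or below nominal, and the stated sample sizes still deliver their stated power under the plan's own assumptions. The gain would be useful mainly if the SD exceeds 4 days. There is a smaller gain for non-inferiority at 10% incidence, where 780 per arm only just reaches 95% power. The change is recommended, but the trial's conclusions do not depend on it.

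**What to change.** Write the following into the SAP:

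- Add centre as a fixed effect to both linear regressions.
- Include centre in the Cox model, as a covariate or as a stratum. In either case, predict each randomised patient's day-30 risk under both arms using that patient's own centre, average over the trial's centre distribution, and take the difference.
- Draw bootstrap samples within centre and arm.
- State in advance how very small centres will be pooled.

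The cost is SAP wording and somewhat more programming for the standardisation and the stratified bootstrap. With up to 10 sites, centre uses at most 10 − 1 = 9 degrees of freedom in about 1,560 patients. Sample size and data collection are unaffected. Fixing this before any data are compared by arm also removes a later analytic choice in an open-label trial.
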